### 9.1 Sample Size Rationale

The sample size and power are driven by the primary endpoint (ie, Nab responses to ancestral strain Novavax vaccine administered as a second (or subsequent) booster after licensed mRNA vaccines and a first ancestral strain Novavax vaccine booster).

MN50 data from Novavax's Study 2019nCoV-301 of around 240 adult participants who received the SARS-CoV-2 rS vaccine on Day 0 and Day 21 in the initial period of primary series or crossover period then received boost dose at Day 0 in the booster period exhibited an 80% confidence upper bound of standard deviation of MN50 GMFR between 28 days after the third active (booster) dose and 14 days after 2nd active dose in log10 scale of 0.61.

The sample size ([Table 5](#)) is based on providing at least 90% power to conclude non-inferiority on Nab titers given the null hypothesis of GMFR ( $\text{GMTDay29-312}/\text{GMTD29-307} \leq 0.67$ ). Here,  $\text{GMTDay29-312}$  is Nab GMT at Day 29 from 2019nCoV-312 and  $\text{GMTD29-307}$  is Nab GMT at Day 29 from Study 307. It is anticipated that these estimates will be equally applicable in the event that a different assay of Nab titers is used for this study.

**Table 5** Summary of Sample Size

GMFR	N
1.0	129
1.1	85
1.2	62
1.3	49
1.4	40
1.5	34

Abbreviation: GMFR=geometric mean fold rise; N=number

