#### 9.3.2 Immunogenicity Analyses

The immunogenicity analysis will be performed using the PP Analysis Set.

For the primary endpoint of Nab responses to the ancestral strain Novavax vaccine administered as a second (or subsequent) booster after licensed mRNA vaccines and a first ancestral strain Novavax vaccine booster, Nab GMTs at Day 1 and Day 29 will be summarized for the group receiving the ancestral strain Novavax vaccine. Nab GMTs along with the corresponding 2-sided 95% CIs, are calculated by exponentiating the corresponding log-transformed means and their 95% CIs. GMFR is defined as the ratio of Nab titers within the group of ancestral strain Novavax vaccine between two different time-points (Day 29 vs. Day 1) to be conducted using t distribution on the log-transformed ratio. Ratio of Nab GMTs for the group receiving the ancestral strain Novavax vaccine between 28 days post first dose (at Day 29) in Study

2019nCoV-312 and 28 days post first dose (at Day 29) in Study 307 among the same participants will be conducted using t distribution on the log-transformed ratio to evaluate non-inferiority. Non-inferiority will be demonstrated if the LB of the 95% CIs for the ratio of Nab GMT at Day 29 between the two booster periods is  $> 0.67$ . If non-inferiority is demonstrated, results will be tested for superiority, defined as the LB of 95% CIs for the ratio of Nab GMTs at Day 29  $> 1.0$ .

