1.2 Sample Size Rationale

The sample size and power are driven by the primary endpoint (ie, Nab responses to ancestral strain Novavax vaccine administered as a second (or subsequent) booster after licensed mRNA vaccines and a first ancestral strain Novavax vaccine booster).

MN₅₀ data from Novavax's study 2019nCoV-301 of around 240 adult participants who received the SARS-CoV-2 rS vaccine on Day 0 and Day 21 in the initial period of primary series or crossover period then received boost dose at Day 0 in the booster period exhibited an 80% confidence upper bound of standard deviation of MN₅₀ GMR between 28 days after the third active (booster) dose and 14 days after 2nd active dose in log₁₀ scale of 0.61.

The sample size (Table 2) is based on providing at least 90% power to conclude non-inferiority on Nab titers given the null hypothesis (Section 7.1) of GMR_{312/307} defined as the ratio of GMT₃₁₂ to GMT₃₀₇ ≤ 0.67 . Here, GMT₃₁₂ is Nab GMT at Day 29 from 2019nCoV-312 and GMT₃₀₇ is Nab GMT at Day 29 from 2019nCoV-307. It is anticipated that these estimates will be equally applicable in the event that a different assay of Nab titers is used for this study.

Table 2: Summary of Sample Size

GMR	N
1.0	129
1.1	85
1.2	62
1.3	49
1.4	40
1.5	34

Note: GMR is defined as the ratio of Day 29 GMT in 2019nCoV-312 to Day 29 GMT in 2019nCoV-307; N is the count of participants.

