3.4 Per-Protocol Analysis Set

The first Per-Protocol Analysis Set (PP1) will include all participants who receive the study vaccine according to the protocol with no receipt of another COVID vaccine (authorized or approved) after Day 1 vaccination, have serology results for baseline and Day 29 available after the vaccination, are PCR negative at baseline for SARS-CoV-2, do not report SARS-CoV-2 infection through Day 29 blood draw, and have no major protocol violations that are considered clinically relevant to impact immunogenicity response as determined by Novavax prior to database lock. This population will reflect the general population many of whom, three years into the pandemic, have experienced SARS-CoV-2 infection, and the immunogenicity measured after study vaccine may reflect “hybrid immunity”. Negative anti-NP result at baseline is not required. Participants with missing anti-NP at baseline will be included in the PP1.

The second Per-Protocol Analysis Set (PP2), intended to represent individuals who have not experienced natural SARS-CoV-2 infection, is defined similarly to PP1 except that it requires a negative baseline anti-N result. Participants with missing baseline anti-N results will be excluded from second Per-Protocol Analysis Set (PP2).

Within the two PP Analysis Sets there are 3 subsets defined separately: Anti-S Protein IgG Serology Subset, Neutralization Assay Subset, and the hACE2 Receptor-binding Inhibition Assay Subset.

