7.2.1 Nab Titers for SARS-CoV-2

As the primary objectives of charactering Nab response to ancestral strain Novavax vaccine administered as a second (or subsequent) booster after licensed mRNA vaccines and a first ancestral strain Novavax vaccine booster, the derived/calculated endpoints of Nab response for **the group receiving ancestral strain Novavax vaccine** will include:

- Nab GMT is calculated as the antilog of the mean of the log-transformed Nab titers. Nab GMT will be summarized by visit day (Days 1 and 29) along with the corresponding 2-sided 95% CIs, by exponentiating the corresponding log-transformed means and their 95% CIs.

- GMFR_{Post/Pre} is calculated as the within-group ratio of post-vaccination Nab GMT at Day 29 to pre-vaccination Nab GMT at the baseline (Day 1).
 - GMFR_{Post/Pre} will be calculated using this formula:

$$GMFR_{Post/Pre} = 10^{\left(\frac{\sum_{i=1}^n \log_{10} \frac{v_{ij}}{v_{ik}}}{n} \right)} = 10^{\frac{\{\sum_{i=1}^n (\log_{10} v_{ij} - \log_{10} v_{ik})\}}{n}}$$

where, for n participants, v_{ij} and v_{ik} are observed immunogenicity titers for subject i at time points j (post-vaccination at Day 29) and k (pre-vaccination at Day 0).

- Below sample SAS code will be conducted using paired t distribution to estimate GMFR_{Post/Pre} and corresponding 95% CIs.

```
proc means data=Nab_D1andD29_nonmissing n mean std t prt clm;
  var diff_aval;
  output out=paired N=n MEAN=mean STDEERR=stderr STD=stddev
  LCLM=lclm UCLM=uclm prt=prt;
run;
```

- GMR_{312/307} defined as the ratio of Nab Geometric Mean Titer (GMT) **28 days after a second (or subsequent) booster dose** of NVX-CoV2373 in Study **2019nCoV-312** versus **28 days after a first booster dose** of NVX-CoV2373 in Study **2019nCoV-307** among the same participants with the corresponding 95% CIs will be conducted using paired t distribution. Non-inferiority will be demonstrated if GMR_{312/307} of Nab titers is higher than 0.67 and superiority will be demonstrated if GMR_{312/307} of Nab titers is higher than 1.0 after non-inferiority is successfully demonstrated.

- GMR_{312/307} will be calculated using this formula:

$$GMR_{312/307} = 10^{\left(\frac{\sum_{i=1}^n \log_{10} \frac{v_{ij}}{v_{ik}}}{n} \right)} = 10^{\frac{\{\sum_{i=1}^n (\log_{10} v_{ij} - \log_{10} v_{ik})\}}{n}}$$

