13 APPENDICES

13.1 Appendix 1: Schedule of Events

Table 7: Schedule of Events

Study Day	-30 to 1 ¹	1 ¹	8	29	Unscheduled Visit	61	91	121	151	181
Window (days)	--	-	+ 3	+ 4	--	± 7	± 15	± 15	± 15	± 15
Study Visit	Screening	1	2	3		Phone Call	Phone Call	Phone Call	Phone Call	EOS Phone Call
Informed consent	X									
Medical history ²	X				X					
Inclusion/exclusion criteria ³	X	X ⁴								
Demographics	X									
Prior/concomitant medications ⁵	X	X ⁴	X	X	X	X	X	X	X	X
Vital sign measurements	X	X ⁴			X					
Urine pregnancy test (WOCBP)	X	X ⁴								
Physical examination ⁶	X	X ⁴			X ⁷					
Baseline ECG		X ⁴								
Nasal swab at clinic for SARS-CoV-2 (PCR) – anterior nares		X ⁴								
Blood sample for anti-NP testing		X ⁴		X						
Blood sampling for SARS-CoV-2 (ELISA for anti S-protein serology, neutralizing antibody titers, and hACE2 receptor-binding inhibition assay)		X ⁴		X						
Vaccination		X ⁸								
Reactogenicity and diary collection		X ^{8,9}	X ⁹							

Table 7: Schedule of Events

Study Day	-30 to 1 ¹	1 ¹	8	29	Unscheduled Visit	61	91	121	151	181
Window (days)	--	-	+ 3	+ 4	--	± 7	± 15	± 15	± 15	± 15
Study Visit	Screening	1	2	3		Phone Call	Phone Call	Phone Call	Phone Call	EOS Phone Call
SAEs	X	X	X	X	X	X	X	X	X	X
All unsolicited AEs		X	X	X	X					
MAAEs and AESIs (including PIMMCs, myocarditis or pericarditis)		X ¹⁰	X ¹⁰	X ¹⁰	X ^{10,11}	X ¹¹				
EOS form ¹²										X

Abbreviations: AESI = adverse event(s) of special interest; eCRF = electronic case report form; EDC = electronic data capture; ELISA = enzyme-linked immunosorbent assay; EOS = end of study; hACE2 = human angiotensin-converting enzyme 2; MAAE = medically attended adverse event; PCR = polymerase chain reaction; PIMMC = potential immune-mediated medical conditions; S = spike (protein); SAE = serious adverse event; SARS-CoV-2 = severe acute respiratory syndrome coronavirus 2; WOCBP = women of childbearing potential.

¹ The Screening visit and Day 1 visit should be combined if feasible at any given study site.

² Significant medical history should be recorded, focusing on ongoing medical conditions.

³ Specific exclusions to study vaccination will be assessed before vaccination. Waivers to enrolling participants with exclusions will not be given.

⁴ Performed prior to study vaccination.

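### PP1 and PP2 set no infection or draw-window rule for the Study 307 Day 29 titer, and ignore Day 29 anti-NP when excluding infection after Study 312 dosing

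*SAP*

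**What the plan says.** SAP 7.2.1 defines the primary ratio as Study 312 Day 29 over Study 307 Day 29, "among the same participants with the corresponding 95% CIs will be conducted using paired t distribution". Half of every observation is therefore a Study 307 sample.

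SAP 3.4 admits participants to PP1 if they meet these conditions:
- vaccination according to protocol, with no other COVID vaccine after Day 1;
- serology, in the words "have serology results for baseline and Day 29 available after the vaccination";
- a negative PCR at baseline;
- no infection after dosing, in the form that they "do not report SARS-CoV-2 infection through Day 29 blood draw";
- no violation judged relevant to immunogenicity.

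PP2 adds a negative baseline anti-N result and drops participants in whom it is missing. SAP 3.4.2 adds only that a neutralization test was done before study vaccination. SAP 3.5.2 treats missed draws and badly out-of-window samples as major deviations but names no Study 307 draw. It also says that a positive baseline PCR does not exclude, which contradicts PP1 in SAP 3.4.

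The schedule in SAP 13.1 has the line "Blood sample for anti-NP testing" marked at Day 1 and Day 29. Neither set definition uses the Day 29 result. SAP 3.2 drops the FAS analysis, so the immunogenicity conclusions rest on PP1 and PP2 (SAP 3.5, 7.2).

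**The concern.** The plan accepts that infection between dose and draw distorts the response, since it removes reported cases in Study 312. It does not state the same rule for the other half of the pair, and in Study 312 it relies on report where a laboratory marker is already collected.

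The two gaps act in opposite directions. An infection before the Study 307 Day 29 draw raises the denominator, lowers the ratio and makes non-inferiority harder to show. A silent infection between Study 312 Day 1 and Day 29 raises the numerator and makes a false non-inferiority claim more likely. The second matters more. PP2 is exposed to it despite its stated aim of representing people without natural infection, because someone anti-N negative at baseline who converts by Day 29 stays in.

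**Working it through.** **1. Can eligibility reach the Study 307 window?** Protocol 5.3 requires the last NVX-CoV2373 dose at least 180 days before the Study 312 dose. Nominal Study 307 Day 29 is 28 days after that dose, so it lies at least 180 − 28 = 152 days before Study 312 Day 1. Protocol 5.4 excludes laboratory-confirmed infection only within 4 months, about 122 days. The exclusion cannot reach the Study 307 window. Protocol 5.4 does remove anyone who had another COVID booster after the Study 307 dose.

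**2. Inputs from the documents.**
- Target: "at least 90% power to conclude non-inferiority on Nab titers" (SAP 1.2), with N=129 at a true ratio of 1.0.
- SD of the paired log10 ratio: 0.61, from Study 301 (Protocol 9.1: "14 days after 2nd active dose in log10 scale of 0.61").
- Margin 0.67, judged on the lower limit of a two-sided 95% CI (Protocol 9.3.2, SAP 7.1), which is one-sided 0.025.

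**3. The plan's own figure.** For a paired t test, the noncentrality is √n × [log10(GMR) − log10(margin)] / SD, and power comes from the noncentral t with n − 1 degrees of freedom. With margin 1/1.5 the required N is 129, 85, 62, 49, 40 and 34, which matches all six rows of SAP Table 2. With 0.67 as written, the first row is 132. At n=129 the noncentrality is then 0.1739 / (0.61/√129) = 0.1739 / 0.0537 = 3.24 and power is 89.5%. The checks below use 0.67.

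**4. Effect of affected pairs.** Let a fraction f of pairs have one titer raised r-fold. The mean log10 ratio moves by f × log10(r), so the ratio is multiplied by r^f if the numerator is affected and by r^(−f) if the denominator is. For example, f=5% and r=4 gives 0.05 × 0.602 = 0.0301, a factor of 1.072 or 0.933. Both f and r are assumptions; the documents give neither.

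| f | r | Factor, numerator / denominator | One-sided error at the margin (numerator affected) | Power at true ratio 1.0 (denominator affected) |
|---|---|---|---|---|
| 0 | – | 1 / 1 | 2.5% | 89.5% |
| 1% | 2 | 1.007 / 0.993 | 2.8% | 88.5% |
| 2% | 2 | 1.014 / 0.986 | 3.2% | 87.3% |
| 2% | 4 | 1.028 / 0.973 | 4.1% | 84.9% |
| 5% | 4 | 1.072 / 0.933 | 8.0% | 75.7% |

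The table holds the SD at 0.61. Adding the mixture variance, SD² + f(1 − f)[log10(r)]², changes the last row to 7.8% and 73.8% and the others by less than one percentage point.

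**5. Cost of losing pairs.** If affected pairs are removed and the true ratio is 1.0, power at margin 0.67 is 87.8% with 122 pairs and 86.1% with 116.

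**The case against.** A reader might infer that the sets screen infection by self-report alone, or that the Study 307 denominator is unscreened. The documents do not support either.

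- PP1 has a laboratory PCR at baseline and PP2 a laboratory anti-N test.
- PP2's anti-N sample is taken after the Study 307 window, so an infection in that window is within what the test targets. It would be missed only if anti-N had waned or never risen.
- Study 307 had its own procedures, which are not in these documents. What can be shown is that this SAP states no rule, not that the samples were never checked.
- A missing Study 307 Day 29 value does not distort the primary ratio. Nothing is imputed (SAP 7.2), and a within-person ratio needs both titers.

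Three further objections have weight. The Study 307 infection gap costs power and cannot by itself produce a false claim; only a mistimed draw could act either way. The sizes are assumption-driven, and at 2% and 2-fold the error is 3.2%, a small change. PP1 also admits hybrid immunity on purpose. That purpose concerns infection before dosing, however, and PP1 still excludes reported infection after it, so it does not explain leaving silent infection in.

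What stands is the missing Study 307 rule, in full for PP1 and in part for PP2, and the unused Day 29 anti-NP result.

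**Conclusion.** The point holds as a gap in the set definitions. SAP 3.4 states no draw-window or interval-infection criterion for the denominator of the primary ratio, and it excludes infection after Study 312 dosing only when reported. Under the assumed 1% to 5% affected and 2- to 4-fold rise, one-sided error at the margin runs from about 2.8% to 8%, and power at a true ratio of 1.0 from about 88% down to 74–76%. The lower end is negligible and the upper end is not; the documents cannot say which applies. These figures rest on n=129, SD 0.61 and margin 0.67, with each gap considered alone. If both occur, the shifts in the ratio partly cancel, but nothing in the plan ensures that they do.

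**What to change.** In SAP 3.4:

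1. **PP2:** also require a negative Study 312 Day 29 anti-NP result.
2. **PP1:** exclude participants who go from anti-NP negative at Day 1 to positive at Day 29. A positive Day 29 result in someone already positive at baseline does not show new infection and should not exclude.
3. **Primary ratio:** require the Study 307 Day 29 sample to be in its window, with no documented infection or excluding deviation between Study 307 Day 1 and Day 29. If Study 307 lacks infection data, say so and use its per-protocol membership instead.
4. **Baseline PCR:** reconcile SAP 3.4 with 3.5.2, so that a positive result either excludes from PP1 and PP2 or does not.

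The cost is SAP wording, a merge with Study 307 data that the sponsor should already hold for the ratio, and a few pairs. Anti-NP at Day 29 is already collected. It will not detect infections too recent to have raised anti-NP, or reinfection in those already positive, so the report-based criterion should stay alongside it.

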#### **6.1.4 Day 29 Visit**

The following activities will occur at the Day 29 visit.

- Prior/concomitant medications
- Blood sampling for SARS-CoV-2 (ELISA for anti-S protein serology, Nab titers, and hACE2 receptor-binding inhibition assay)
- Blood sampling for anti-NP testing
- Recording of unsolicited AEs, SAEs, MAAEs, and AESIs (including PIMMCs and myocarditis or pericarditis). See [Table 3](#) for symptoms of myocarditis or pericarditis and [Table 4](#) for instructions for follow-up.

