3.5.2 Major Protocol Deviations Assessment

Protocol deviations deemed to indicate clear violations of GCP and/or subject consent; or to have a likely effect on the primary and secondary immunogenicity outcomes will exclude those participants from both PP analysis sets (PP1 and PP2). This determination will be made by the NOVAVAX Clinical Lead prior to database freeze or lock.

When interim analysis (Day 29 primary analysis) DB freezes or Day 181 final analysis DB locks, Syneos will assess protocol deviations and create a consensus final protocol deviations assessment file. NOVAVAX team will determine whether PDs are major and make the final decision of which participants will be excluded from the PP analysis based on the PD listing from Syneos.

In general, inclusion/exclusion criteria failure, receipt of prohibited therapies, receipt of another COVID vaccine (authorized or approved), missed blood draw and laboratory samples obtained sufficiently outside visit windows to likely impact the result will be deemed “major” deviations relevant for analysis. Criteria for this determination will be established prior to review of PDs. Any positive PCR or anti-NP result obtained at baseline Day 1 is not exclusionary and will not be considered a major PD.

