7.2 Analysis of Primary/Secondary Endpoints of Immunogenicity

The immunogenicity analysis will be performed using the first PP Analysis Set (PP1) and the second PP Analysis Set (PP2). No missing data will be imputed. Titers/ELISA Units reported below the lower limit of quantification (LLOQ) will be set to half that limit (ie, if LLOQ=10, then 10/2 = 5) for use in computations.

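### PP2 is meant to hold people without natural infection, but the scheduled Day 29 anti-NP result is never used, so unreported infections after Day 1 stay in it

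*SAP*

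**What the plan says.** Anti-NP blood is drawn twice. Protocol 6.1.4 lists "Blood sampling for anti-NP testing" among the Day 29 activities. The schedules of events (protocol Table 1; SAP Table 7, row "Blood sample for anti-NP testing") mark Day 1 and Day 29. The PCR swab is scheduled on Day 1 only.

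SAP 3.4 defines two per-protocol sets:

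- **PP1** requires a negative PCR at baseline and participants who "do not report SARS-CoV-2 infection through Day 29 blood draw". On serology it says "Negative anti-NP result at baseline is not required".
- **PP2** is "intended to represent individuals who have not experienced natural SARS-CoV-2 infection". It "is defined similarly to PP1 except that it requires a negative baseline anti-N result", and participants with a missing baseline result are left out.

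SAP 3.5.2 on major deviations speaks only of Day 1 results: "Any positive PCR or anti-NP result obtained at baseline Day 1 is not exclusionary and will not be considered a major PD". Analysis on the FAS has been dropped (SAP 3.2), so PP1 and PP2 are the only sets for immunogenicity (SAP 7.2). SAP 11.2 provides for no covariate adjustment.

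**The concern.** The plan has already decided that infection before the Day 29 draw should remove a participant, because reported infections do. It has also decided that PP2 should stand for people without natural infection. For the weeks after Day 1, however, it relies on self-report alone and leaves aside a laboratory result that it schedules for every participant.

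The vaccine antigen is the spike protein (protocol 2.1.1), so vaccination should not itself turn anti-NP positive. A change from negative to positive is therefore evidence of infection in the window. Such an infection would tend to raise the Study 312 Day 29 Nab, IgG and hACE2 values and, through them, the Study 312 seroconversion rates. These values form the numerator of the primary ratio, tested against 0.67 and then 1.0, and one side of the seroconversion comparison, tested against −10%.

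**Working it through.** **1. Does anything use the Day 29 anti-NP result?** I take anti-NP and anti-N, both used in SAP 3.4, to be the same test.

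| Place | Use of anti-NP |
|---|---|
| Protocol 9.2.4 (PP set) | none |
| SAP 3.4, PP1 | baseline result only; negative not required |
| SAP 3.4, PP2 | baseline result only; negative required |
| SAP 3.5.2 (major deviations) | baseline result only |
| SAP 5 (baseline characteristics) | none |
| SAP 7.2.1–7.2.3 (Nab, IgG, hACE2) | none beyond PP1 and PP2 |
| SAP 7.4, 8, 11 | none |

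A Day 1 negative, Day 29 positive participant with no reported infection thus meets every stated PP2 condition on infection.

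**2. The plan's own figure.** Inputs from SAP 1.2 and protocol 9.1: SD of the paired log10 ratio 0.61, power 90%, true GMR 1.0, N = 129. A paired t calculation with one-sided alpha 0.025 and margin 1/1.5 reproduces Table 2 exactly (129, 85, 62, 49, 40, 34). With the margin as printed, 0.67, it gives 132, 87, 63, 50, 41, 34, and the power at 129 is 0.895. The table is sound to within three participants, so n = 129 and SD 0.61 serve below.

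**3. Effect on the numerator.** By SAP 7.2.1, log10 GMR is the mean of log10(v312/v307). If a share p has v312 multiplied by f, the mean moves by p·log10(f), so the GMR is multiplied by f^p. Example: p = 5%, f = 4 gives 0.05 × 0.602 = 0.0301, and 10^0.0301 = 1.072. Both p and f are assumptions; the documents give neither.

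| p | f = 2 | f = 4 | f = 8 |
|---|---|---|---|
| 2% | 1.014 | 1.028 | 1.042 |
| 5% | 1.035 | 1.072 | 1.110 |
| 10% | 1.072 | 1.149 | 1.231 |

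A 10% lift needs p = ln(1.1)/ln(f): 13.8% at f = 2 and 6.9% at f = 4.

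**4. Effect on the ratio.** The same reasoning applies to the denominator. With silent infection in both windows, the multiplier is f312^p312 / f307^p307, which is 1 when the two windows are alike. The SAP states no infection rule for Day 1 to Day 29 of Study 307, so nothing in the documents fixes the second factor.

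**5. Error rate if only the Study 312 window is affected.** Simulation of the paired t lower bound: n = 129, SD 0.61, 40,000 runs per cell, GMR among the uninfected exactly 0.67. The chance of declaring non-inferiority (nominal 0.025) was:

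| p | f = 2 | f = 4 |
|---|---|---|
| 0 | 0.025 | 0.023 |
| 2% | 0.034 | 0.040 |
| 5% | 0.044 | 0.077 |
| 10% | 0.078 | 0.183 |

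The same rates apply to the superiority test at a true GMR of 1.0. They are conditional on no silent infection in the Study 307 window.

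**6. Cost of excluding converters.** From a set of 129, power at GMR 1.0 with margin 0.67 goes from 0.895 to 0.888 (2% excluded, n = 126), 0.880 (5%, n = 123) or 0.861 (10%, n = 116).

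**The case against.** Several points count against making much of this.

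- **Safeguards keep p down.** Participants must be PCR negative on Day 1, unsolicited adverse events are collected for 28 days (protocol 8.1.3), and participants are asked about changes in health at each contact (protocol 8.1.1). Only unreported or symptom-free infection within about four weeks remains. This stands: nothing in the documents supports a share as high as 10%.
- **The size of f is unknown.** It is the extra rise on top of a booster response, measured against the ancestral strain. This also stands, which is why f = 2 belongs in the table.
- **PP1 accepts past infection by design.** The SAP describes it as reflecting hybrid immunity. Conversion can be read only in baseline negatives, so a mandatory exclusion would give PP1 two infection rules according to baseline serology. This stands and argues for a sensitivity analysis in PP1 rather than an exclusion.
- **The sponsor could act without a new rule.** The reporting condition might be read to cover laboratory results, or converters might be dropped as major violations. Neither is convincing. The plain sense of the condition is participant report, and infection is not a departure from study procedures.

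A reader might infer that the omission tilts the trial towards non-inferiority and superiority. The documents do not support that as a net statement: silent infection in the Study 307 window would raise the denominator, and neither rate is known. Nor do they support a larger bias in PP2 than in PP1. The formula f^p is the same for both sets, and no document gives a higher p or f for PP2. What is greater in PP2 is the mismatch with its stated purpose.

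**Conclusion.** The gap is real. PP2's stated intent is not carried through to the Day 29 draw, although the sample that would do so is already scheduled. Unreported infections between Day 1 and Day 29 remain in both sets and would raise the Study 312 values.

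For assumed p of 2–10% and f of 2–8, the numerator is multiplied by about 1.01 to 1.23. At p near 2% the effect is small (1.01 to 1.04); it becomes material only from about 5%, and then depends on f. These figures describe the numerator. The direction and size of the net effect on GMR 312/307 cannot be settled from the documents. The case for a change rests on PP2 not matching its own definition and on the low cost of repair, not on a demonstrated bias.

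**What to change.** In SAP 3.4 and the related tables:

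1. **PP2:** require a negative anti-NP result at both Day 1 and Day 29. Extend the existing rule for missing baseline results to a missing Day 29 result.
2. **Report:** tabulate by vaccine group the number who convert from Day 1 negative to Day 29 positive, and how many of these had reported an infection.
3. **PP1:** keep the definition, and add a sensitivity analysis of the GMR and SCR comparisons without the converters.

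While editing, reconcile SAP 3.5.2, which treats a positive Day 1 PCR or anti-NP as not exclusionary, with SAP 3.4, which requires a negative PCR for PP1 and also a negative anti-N for PP2. If Day 29 results have already been seen, label the new rule as post hoc.

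The cost is SAP wording and programming; no visit or sample is added. A few pairs are lost. To keep 129 evaluable after losing 2%, 5% or 10% takes 132, 136 or 144 participants (129/0.98, 129/0.95, 129/0.90, rounded up), within the planned 100–150. PP2 will start smaller, and the documents do not give its size. At 80 or 60 pairs, power at GMR 1.0 is already 0.712 or 0.584 before this exclusion.

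Two limits remain. Infections shortly before Day 29 may not yet have turned anti-NP positive, and PP1 participants who are anti-NP positive or missing at baseline are still screened by self-report alone.
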